8.2. Sample size consideration

8.2.1. Assumptions:

A target to obtain at least 500 subjects/site still active at the end of the first year of the study *is planned*. *Since* subjects might leave the study due to a variety of reasons, e.g. moving away geographically, sample size is increased to allow for this. On the basis of

an annual drop-out rate between 15 and 20%, approximately 600 subjects/site will be enrolled at the beginning of this study. The recruitment will be cluster sampling, i.e. the unit of sampling will be the households. Different areas where the FHP has been fully implemented or where access to the community is already established by a government program will be first selected, followed by a selection of households in the respective areas. All subjects in each household will be invited for recruitment to the study.

New sites will start enrolling subjects preferably during study Year 2. The target is to enrol approximately 600 subjects per additional site. Replacement subjects may be recruited in order to maintain at least 500 subjects/site still active at the beginning of the next dengue season.

In order to better represent the Brazilian population distribution, subjects enrolled in the expansion cohort should be composed of at least 30% of subjects younger than 18 years old and should not exceed 20% of adults 50 years or older. Subjects enrolled as replacement subjects for the initial and expansion cohort will be recruited to approach as much as possible a minimal representation of 30% of subjects younger than 18 years old and a maximal representation of 20% for adults 50 years or older.

The total study duration per site will last approximately 4 years for the initial cohort and approximately 3 years for the expansion cohort, and new subjects will be enrolled if the number of subjects still active in the study is below 500/site after year 1 and at the beginning of each additional study year/season.

Between 2007 and 2010, the average incidence of reported dengue cases in the Brazilian population was about 0.3% per year (or 0.003 cases per person per year). Assuming an underreporting factor of 3 (Brazil MoH, 2011) the average incidence of dengue is expected to be about 1% per year (or 0.01 cases per person per year).

8.2.2. Estimating design effect and precision

The normal approximation of the Poisson distribution was used for calculating 95% CI for this cluster design. The variance was adjusted for a design effect of 1.8 to account for the between-cluster variability.

The design effect measures the increase in the standard error of the estimate due to the sampling design used and is given by: $D = 1 + (b - 1) \rho$, where ρ is the rate of homogeneity (a measure of variability and equivalent to the “intra-cluster correlation”) and b is the average number of subjects sampled per household. Here we assumed b to be 3. Although in theory ρ can have a value up to 1, in practice values higher than 0.4 are uncommon. We used a conservative estimate of 0.4 for this study (Bennett, 1991). The design effect is then estimated to 1.8.

8.2.3. Expected precision of incidence rate estimates

Table 15 shows the 95% CI for a range of expected incidences based on the Poisson distribution (exact method, normal approximation and the normal approximation accounting for a design effect of 1.8) in different scenarios. The scenarios were defined according to the following criteria:

- Number of subjects enrolled at the beginning of the study (for some sites it will be the second year). At season level and for all sites: 2000, 4000, 1800, 3600, 1500, 3000. For all seasons and for all sites: 4000, 3600 and 3000. At season level and site level: 600 and 500.
- Number of years of follow-up. At study level: 1 or 4 years, but half of the sites will be followed for 3 years and this is taken into account for the calculations. At site level: 1, 3 or 4 years.
- Overall incidences: 3, 6, 9, 12 or 15 events per 1000 person-years.

With an overall sample size of a minimum of about 3,600 subjects enrolled and a follow-up period of one year, the 95% confidence interval (CI) for an expected incidence of dengue of 9 cases per 1000 person-years using a cluster design is [4.7 ; 13.3]. With 3600 subjects enrolled, 4 years of follow-up and new enrolments to keep the number of subjects above 3000 at the beginning of each subsequent season, the 95% CI is [6.3 ; 11.7].

CONFIDENTIAL

116606 (EPI-DENGUE-006 BOD BR)
Protocol Amendment 4 Final

Table 15 Precision of the expected incidences of dengue for a single cohort of subjects in Brazil

	Cohort size	Number of years	Number of person-years	Number of cases	Incidence of dengue (per 1000 person-years)	95% CI of incidence rate (n / 1000 P-Y)						New enrolment		
						Exact (Poisson)		Normal approx		Normal approx with design effect		After Y1	After Y2	After Y3
						Lower	Upper	Lower	Upper	Lower	Upper			
Overall	2000	1	1845.9	6	3.0	1.0	6.7	0.5	5.5	-0.4	6.4			
	2000	1	1845.9	11	6.0	3.0	10.7	2.5	9.5	1.3	10.7			
	2000	1	1845.9	17	9.0	5.2	14.5	4.7	13.3	3.2	14.8			
	2000	1	1845.9	22	12.0	7.5	18.1	7.0	17.0	5.3	18.7			
	2000	1	1845.9	28	15.0	9.9	21.7	9.4	20.6	7.5	22.5			
	4000	1	3691.9	11	3.0	1.5	5.4	1.2	4.8	0.6	5.4			
	4000	1	3691.9	22	6.0	3.8	9.1	3.5	8.5	2.6	9.4			
	4000	1	3691.9	33	9.0	6.2	12.6	5.9	12.1	4.9	13.1			
	4000	1	3691.9	44	12.0	8.7	16.1	8.5	15.5	7.3	16.7			
	4000	1	3691.9	55	15.0	11.3	19.5	11.0	19.0	9.7	20.3			
	4000	4	9086.6	27	3.0	2.0	4.4	1.9	4.1	1.5	4.5			327
	4000	4	9086.6	55	6.0	4.5	7.8	4.4	7.6	3.9	8.1			327
	4000	4	9086.6	82	9.0	7.2	11.2	7.0	11.0	6.4	11.6			327
	4000	4	9086.6	109	12.0	9.9	14.5	9.7	14.3	9.0	15.0			327
	4000	4	9086.6	136	15.0	12.6	17.7	12.5	17.5	11.6	18.4			327
	1800	1	1661.3	5	3.0	0.9	7.2	0.4	5.6	-0.5	6.5			
	1800	1	1661.3	10	6.0	2.8	11.1	2.3	9.7	1.0	11.0			
	1800	1	1661.3	15	9.0	5.0	14.9	4.4	13.6	2.9	15.1			
	1800	1	1661.3	20	12.0	7.3	18.6	6.7	17.3	4.9	19.1			
	1800	1	1661.3	25	15.0	9.7	22.1	9.1	20.9	7.1	22.9			
3600	1	3322.7	10	3.0	1.4	5.6	1.1	4.9	0.5	5.5				
3600	1	3322.7	20	6.0	3.6	9.3	3.4	8.6	2.5	9.5				

CONFIDENTIAL

116606 (EPI-DENGUE-006 BOD BR)
Protocol Amendment 4 Final

	Cohort size	Number of years	Number of person-years	Number of cases	Incidence of dengue (per 1000 person-years)	95% CI of incidence rate (n / 1000 P-Y)						New enrolment		
						Exact (Poisson)		Normal approx		Normal approx with design effect		After Y1	After Y2	After Y3
						Lower	Upper	Lower	Upper	Lower	Upper			
	3600	1	3322.7	30	9.0	6.1	12.9	5.8	12.2	4.7	13.3			
	3600	1	3322.7	40	12.0	8.6	16.3	8.3	15.7	7.0	17.0			
	3600	1	3322.7	50	15.0	11.1	19.8	10.8	19.2	9.4	20.6			
	3600	4	8611.3	26	3.0	2.0	4.4	1.8	4.2	1.4	4.6		170	450
	3600	4	8611.3	52	6.0	4.5	7.9	4.4	7.6	3.8	8.2		170	450
	3600	4	8611.3	78	9.0	7.1	11.2	7.0	11.0	6.3	11.7		170	450
	3600	4	8611.3	103	12.0	9.8	14.5	9.7	14.3	8.9	15.1		170	450
	3600	4	8611.3	129	15.0	12.5	17.8	12.4	17.6	11.5	18.5		170	450
	1500	1	1384.5	4	3.0	0.8	7.6	0.1	5.9	-0.9	6.9			
	1500	1	1384.5	8	6.0	2.6	11.7	1.9	10.1	0.5	11.5			
	1500	1	1384.5	12	9.0	4.7	15.6	4.0	14.0	2.3	15.7			
	1500	1	1384.5	17	12.0	6.9	19.3	6.2	17.8	4.3	19.7			
	1500	1	1384.5	21	15.0	9.2	22.9	8.5	21.5	6.3	23.7			
	3000	1	2768.9	8	3.0	1.3	5.9	1.0	5.0	0.3	5.7			
	3000	1	2768.9	17	6.0	3.5	9.7	3.1	8.9	2.1	9.9			
	3000	1	2768.9	25	9.0	5.8	13.3	5.5	12.5	4.3	13.7			
	3000	1	2768.9	33	12.0	8.3	16.8	7.9	16.1	6.5	17.5			
	3000	1	2768.9	42	15.0	10.8	20.3	10.4	19.6	8.9	21.1			
	3000	4	8306.7	25	3.0	1.9	4.4	1.8	4.2	1.4	4.6	225	450	450
	3000	4	8306.7	50	6.0	4.4	7.9	4.3	7.7	3.8	8.2	225	450	450
	3000	4	8306.7	75	9.0	7.1	11.3	7.0	11.0	6.3	11.7	225	450	450
	3000	4	8306.7	100	12.0	9.8	14.6	9.6	14.4	8.8	15.2	225	450	450
	3000	4	8306.7	125	15.0	12.5	17.9	12.4	17.6	11.5	18.5	225	450	450

CONFIDENTIAL

116606 (EPI-DENGUE-006 BOD BR)
Protocol Amendment 4 Final

	Cohort size	Number of years	Number of person-years	Number of cases	Incidence of dengue (per 1000 person-years)	95% CI of incidence rate (n / 1000 P-Y)						New enrolment		
						Exact (Poisson)		Normal approx		Normal approx with design effect		After Y1	After Y2	After Y3
						Lower	Upper	Lower	Upper	Lower	Upper			
Site	600	1	553.8	2	3.0	0.2	12.3	-1.6	7.6	-3.1	9.1			
	600	1	553.8	3	6.0	1.2	17.0	-0.5	12.5	-2.7	14.7			
	600	1	553.8	5	9.0	2.7	21.4	1.1	16.9	-1.6	19.6			
	600	1	553.8	7	12.0	4.6	25.1	2.9	21.1	-0.2	24.2			
	600	1	553.8	8	15.0	6.5	29.2	4.8	25.2	1.3	28.7			
	600	3	1486.0	4	3.0	0.8	7.5	0.2	5.8	-0.7	6.7		67	
	600	3	1486.0	9	6.0	2.7	11.5	2.1	9.9	0.7	11.3		67	
	600	3	1486.0	13	9.0	4.8	15.3	4.2	13.8	2.5	15.5		67	
	600	3	1486.0	18	12.0	7.1	19.0	6.4	17.6	4.5	19.5		67	
	600	3	1486.0	22	15.0	9.4	22.6	8.8	21.2	6.6	23.4		67	
	600	4	1947.5	6	3.0	1.0	6.7	0.6	5.4	-0.3	6.3		67	75
	600	4	1947.5	12	6.0	3.1	10.6	2.6	9.4	1.4	10.6		67	75
	600	4	1947.5	18	9.0	5.3	14.3	4.8	13.2	3.3	14.7		67	75
	600	4	1947.5	23	12.0	7.6	17.9	7.1	16.9	5.5	18.5		67	75
	600	4	1947.5	29	15.0	10.1	21.5	9.6	20.4	7.7	22.3		67	75
	500	1	461.5	1	3.0	0.1	14.3	-2.0	8.0	-3.7	9.7			
	500	1	461.5	3	6.0	1.0	18.6	-1.1	13.1	-3.5	15.5			
	500	1	461.5	4	9.0	2.5	22.7	0.3	17.7	-2.6	20.6			
	500	1	461.5	6	12.0	4.2	26.8	2.0	22.0	-1.4	25.4			
	500	1	461.5	7	15.0	5.8	31.2	3.8	26.2	0.0	30.0			
	500	3	1384.5	4	3.0	0.8	7.6	0.1	5.9	-0.9	6.9	75	75	
	500	3	1384.5	8	6.0	2.6	11.7	1.9	10.1	0.5	11.5	75	75	
	500	3	1384.5	12	9.0	4.7	15.6	4.0	14.0	2.3	15.7	75	75	
	500	3	1384.5	17	12.0	6.9	19.3	6.2	17.8	4.3	19.7	75	75	

CONFIDENTIAL

116606 (EPI-DENGUE-006 BOD BR)
Protocol Amendment 4 Final

	Cohort size	Number of years	Number of person-years	Number of cases	Incidence of dengue (per 1000 person-years)	95% CI of incidence rate (n / 1000 P-Y)						New enrolment		
						Exact (Poisson)		Normal approx		Normal approx with design effect		After Y1	After Y2	After Y3
						Lower	Upper	Lower	Upper	Lower	Upper			
	500	3	1384.5	21	15.0	9.2	22.9	8.5	21.5	6.3	23.7	75	75	
	500	4	1845.9	6	3.0	1.0	6.7	0.5	5.5	-0.4	6.4	75	75	75
	500	4	1845.9	11	6.0	3.0	10.7	2.5	9.5	1.3	10.7	75	75	75
	500	4	1845.9	17	9.0	5.2	14.5	4.7	13.3	3.2	14.8	75	75	75
	500	4	1845.9	22	12.0	7.5	18.1	7.0	17.0	5.3	18.7	75	75	75
	500	4	1845.9	28	15.0	9.9	21.7	9.4	20.6	7.5	22.5	75	75	75

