2. OBJECTIVES

2.1. Primary objective

- To estimate the incidence of laboratory-confirmed symptomatic dengue infection in the study population by year/season.

Refer to Section 8.1.1 for the primary endpoint.

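### The one-year precision of [4.7 ; 13.3] in Protocol Section 8.2.3 needs 3600 subjects in one season, which the planned staggered enrolment does not provide

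*Protocol*

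**What the plan says.** The primary objective (Protocol Section 2.1) is "To estimate the incidence of laboratory-confirmed symptomatic dengue infection in the study population by year/season".

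Section 8.2.3 defines the scenarios behind Table 15. For one-year precision it lists the sizes as follows: "At season level and for all sites: 2000, 4000, 1800, 3600, 1500, 3000". The text then singles out one of these sizes in a sentence that opens "With an overall sample size of a minimum of about 3,600 subjects enrolled and a follow-up period of one year, the 95% confidence interval". At a rate of 9/1000, and with the design effect, the limits it reports are [4.7 ; 13.3]. No other one-year interval appears in the text.

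Enrolment is in two waves of about 1800, the initial and the expansion cohort (Section 3). On timing, Section 8.2.1 says: "New sites will start enrolling subjects preferably during study Year 2". Section 8.2.1 also assumes 15 to 20% annual drop-out, and Section 7.3 replaces lost subjects to keep at least 500 per site. With six sites that is a floor of 3000. Table 1 accordingly shows each cohort at 1800 on enrolment and at least 1500 in later years.

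**The concern.** The objective is a rate for each year or season, so the relevant precision is that of one season's person-years. The one-year sentence uses both waves at full enrolment size. They reach that size in different years, and by the time the second wave joins, the first has had a year of drop-out.

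The study is meant to check attack-rate assumptions for future efficacy trials, and Section 1.2 stresses that incidence varies strongly from year to year. A trial planner reading Section 8.2.3 would take [4.7 ; 13.3] as what one season can deliver. If no planned season holds that many subjects, the quoted precision is too favourable for the primary estimand, most of all in Year 1.

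**Working it through.** **Method stated in the plan (Section 8.2.2).** Intervals come from a normal approximation to Poisson counts, and clustering enters through the variance: "The variance was adjusted for a design effect of 1.8 to account for the between-cluster variability". So the half-width per 1000 person-years (PY) is 1.96 × √(1.8 × 0.009 / PY) × 1000 at a rate of 9/1000.

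**Reproducing the headline.** Table 15's person-years correspond to 15% annual drop-out at a constant rate: PY per subject = 0.15 / (−ln 0.85) = 0.92297. Then 3600 × 0.92297 = 3322.7, as printed. The half-width is 1.96 × √(1.8 × 0.009 / 3322.7) × 1000 = 4.33, giving [4.7 ; 13.3]. The headline reproduces.

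**Subjects at the start of each season**, with 1800 enrolled in Year 1, 1800 more in Year 2, 15% drop-out and replacement to 3000:
- Year 1: 1800.
- Year 2: 1800 × 0.85 + 1800 = 1530 + 1800 = 3330.
- Year 3: 3330 × 0.85 = 2830.5, topped up by 169.5 to 3000.
- Year 4: 3000 × 0.85 = 2550, topped up by 450 to 3000.

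**Check against the plan's own figures.** The 3600-subject four-year row of Table 15 prints 8611.3 PY, with 170 new enrolments after Year 2 and 450 after Year 3. (3330 + 3000 + 3000) × 0.92297 = 8611.3, and the top-ups above are 169.5 and 450. Table 11 independently anticipates 1530 initial-cohort subjects at Visit 3. The multi-year row therefore models the stagger; the one-year headline does not.

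**Precision by season** at 9/1000, design effect 1.8, 15% drop-out:

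| Season | Subjects | PY | Expected cases | Half-width | 95% CI | Against 4.33 |
|---|---|---|---|---|---|---|
| Headline | 3600 | 3322.7 | 30 | 4.33 | [4.7 ; 13.3] | – |
| Year 1 | 1800 | 1661.3 | 15 | 6.12 | [2.9 ; 15.1] | +41% |
| Year 2 | 3330 | 3073.5 | 28 | 4.50 | [4.5 ; 13.5] | +4% |
| Years 3 and 4 | 3000 | 2768.9 | 25 | 4.74 | [4.3 ; 13.7] | +10% |

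**Sensitivity.** At 20% drop-out the initial cohort falls to its floor of 1500, so Year 2 starts with 3300. The intervals become [2.8 ; 15.2], [4.4 ; 13.6] and [4.2 ; 13.8]. If replacement is applied site by site, the three expansion sites still hold 510 each in Year 3, so the total is 1530 + 1500 = 3030; the interval is still [4.3 ; 13.7].

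**Side observation.** The four-year total has three yearly terms and leaves out Year 1. Adding it gives 8611.3 + 1661.3 = 10272.6 PY and [6.5 ; 11.5], against the printed [6.3 ; 11.7]. That figure errs on the wide side and does not change this point.

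**The case against.** Four points can be made for the plan.

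- **The arithmetic is right.** This stands. A reader might infer a miscalculation, but the interval follows exactly from 3600 subjects and one year. The fault is the scenario chosen for the sentence.
- **The right intervals are already printed.** This largely stands. A reader might infer that every by-season interval in the protocol is too narrow. The documents do not support that: Table 15 has one-year rows for 1800 ([2.9 ; 15.1]) and 3000 ([4.3 ; 13.7]), which fit Year 1 and Years 3 and 4. Only the Year 2 row is missing. What the text lacks is any link from rows to seasons.
- **The stagger is disclosed.** Section 8.2.3 notes that some sites begin in the second year, and the sentence speaks of a year of follow-up, so 3600 could mean both waves' first years pooled. That reading is possible, but a pooled first year is not a season, and the same section labels the size as season level.
- **More subjects are allowed.** A reader might infer that the plan can never hold 3600 in a season. That is too strong. The total of 3600 is a minimum, 500 per site is a floor, and the Year 2 start is only preferred. Table 15's 4000-subject four-year row (9086.6 PY) equals (3700 + 3145 + 3000) × 0.92297; its Year 2 would start with 3700 subjects, about 3415 PY, and again give [4.7 ; 13.3]. The point therefore holds for the planned 1800 + 1800 with replacement to the floor, and not for every permitted enrolment.

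The practical weight is also limited: the analyses are descriptive, and SAP Amendment 1 drops the by-season analyses and keeps calendar years. A calendar-year rate still depends on the subjects present in that year, so the mismatch remains.

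**Conclusion.** The one-year precision sentence is wrong as a description of single-season precision under the planned design. No planned season starts with 3600 subjects, and each is less precise than [4.7 ; 13.3]. Year 1 is materially worse, with half the expected cases and an interval 41% wider. In Years 2 to 4 the loss is small: 4 to 10%, or 0.2 to 0.4 per 1000 at each limit.

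This rests on about 3600 enrolled in two equal waves, the second starting in Year 2, 15% drop-out, replacement to 500 per site, a rate of 9/1000 and a design effect of 1.8.

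The study as run points the same way. SAP Amendment 1 (Sections 2.1 and 7) shows two, three, four and five sites covering the 2015 to 2018 seasons, with the sixth site never opened. If each site held 500 to 600 subjects (an assumption), 2018 would have 2500 to 3000 subjects and an interval between [3.8 ; 14.2] and [4.3 ; 13.7].

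**What to change.** In Section 8.2.3, replace the one-year sentence with the season-specific intervals at 9/1000: Year 1, about 1800 subjects, [2.9 ; 15.1]; Year 2, about 3330, [4.5 ; 13.5]; Years 3 and 4, about 3000, [4.3 ; 13.7]. State the assumptions next to them: 3600 enrolled, second wave in Year 2, 15% drop-out, replacement to the floor.

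In Table 15, add a 3330-subject one-year row. Keep the 3600 and 4000 one-year rows, which are legitimate scenarios, but mark them as the two waves' first follow-up years pooled and not the starting size of any single season when that total is enrolled in staggered waves.

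Since the study has ended, the study report should not cite [4.7 ; 13.3] as the planned precision of a single year or season.

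The cost is a sentence and a few table entries. The stated single-season precision becomes less favourable; no subjects, procedures or analyses change.

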8.5.2. Analysis of primary and secondary endpoints

The following analyses will be performed overall and by DENV type, study site, gender and age-group previous dengue exposure (Yes = DENV IgG antibodies at previous visit and No = no DENV IgG antibodies at previous visit):

- Incidence rate of laboratory-confirmed symptomatic dengue infection with 95% CI for each season separately: the numerator will be the number of subjects with lab-confirmed symptomatic dengue infection during the season (between the visits scheduled before and after the season). The denominator will be the total person-years at risk, i.e. from the visit scheduled before the season until the first RT-qPCR confirmed symptomatic dengue infection during the season, the next scheduled visit or the subject's withdrawal, whichever comes first.
- Incidence rate of laboratory-confirmed symptomatic dengue infection with 95% CI all seasons combined: the numerator will be the number of subjects with lab-confirmed symptomatic dengue infection during the study period. The denominator will be the total person-years at risk, i.e. from enrolment until the first RT-qPCR confirmed symptomatic dengue infection, the end of the study or the subject's withdrawal, whichever comes first.

The following analyses will be performed by study site, gender and age-group previous dengue exposure (primary or secondary):

- Incidence rate of laboratory confirmed or probable symptomatic dengue infections with 95% CI for each season separately and overall. The numerator will be the number of subjects with symptomatic dengue infection (including laboratory-confirmed and probable cases) during the period. The denominator will be the total person-years at risk.
- Incidence rate of probable symptomatic dengue infection with 95% CI for each season separately and overall. The numerator will be the number of subjects with probable symptomatic dengue infection. The denominator will be the total person-years at risk.

The following analyses will be performed by study site, gender and age-group:

- The proportion of subjects with primary inapparent dengue infection at each subsequent scheduled visit (not at enrolment) with 95% CI will be calculated as the number of dengue IgG positive cases and at the visit divided by the total number of subjects IgG negative at the previous visit.

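### The overall 4-year rows of protocol Table 15 omit the initial cohort's first year of person-time, so the all-seasons precision quoted in 8.2.3 is understated

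*Protocol*

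**What the plan says.** Section 8.2.1 plans follow-up of "approximately 4 years for the initial cohort and approximately 3 years for the expansion cohort" and assumes "an annual drop-out rate between 15 and 20" per cent. New sites start preferably in study Year 2. Section 8.2.3 says of the study-level rows that "half of the sites will be followed for 3 years and this is taken into account for the calculations".

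Section 8.2.2 gives the method: "The normal approximation of the Poisson distribution was used for calculating 95% CI for this cluster design", and "The variance was adjusted for a design effect of 1.8 to account for the between-cluster variability".

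The text of 8.2.3 then gives two precision figures at 9 cases per 1000 person-years. For 3600 subjects and one year, the interval for an "expected incidence of dengue of 9 cases per 1000 person-years using a cluster design is [4.7 ; 13.3"]. For 3600 subjects and 4 years, the wording is "new enrolments to keep the number of subjects above 3000 at the beginning of each subsequent season, the 95% CI is [6.3 ; 11.7"].

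The all-seasons rate to which the second figure applies is defined in section 8.5.2, where the denominator is "total person-years at risk, i.e. from enrolment until the first RT-qPCR confirmed symptomatic dengue infection", the end of the study or withdrawal.

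**The concern.** If the initial sites are followed for 4 years and the expansion sites for 3, the overall 4-year rows should be close to three 4-year site rows plus three 3-year site rows. They are well below that sum, and the gap in the 3000-subject row equals one year of follow-up for 1500 subjects.

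Section 8.2.3 gives only two precision figures in its text, and one of them is affected. A reader who compares the person-years achieved with 8611.3 would use a benchmark about 16% below what the follow-up plan implies.

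**Working it through.** **Check from printed figures only.** Table 15 gives a 500-subject site 1845.9 person-years over 4 years and 1384.5 over 3 years.

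- Three of each: 3 × 1845.9 + 3 × 1384.5 = 5537.7 + 4153.5 = 9691.2.
- Printed overall row, 3000 subjects, 4 years: 8306.7.
- Gap: 9691.2 − 8306.7 = 1384.5, which is the table's one-year figure for 1500 subjects.

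No drop-out rate is needed for this.

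**Reproducing the table.** With annual drop-out d and constant loss within the year, person-years per starting subject are f = d / (−ln(1 − d)). At d = 0.15, f = 0.92297. This returns the one-year rows: 500 gives 461.5, 1800 gives 1661.3, 3600 gives 3322.7. The initial half enters in Year 1 and the expansion half at the start of Year 2. Survivors are topped up to 1500 after Year 1 and to 3000 after Years 2 and 3.

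For 3600 subjects:

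- Year 1: 1800 start, 1661.3 person-years; 1800 × 0.85 = 1530 remain, no top-up.
- Year 2: 1530 + 1800 = 3330 start, 3073.5 person-years; 2830.5 remain, top-up 169.5 (printed 170).
- Year 3: 3000 start, 2768.9 person-years; 2550 remain, top-up 450 (printed 450).
- Year 4: 3000 start, 2768.9 person-years.

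| Subjects | Year 1 | Years 2 to 4 | Sum of Years 2–4 | Printed | Sum of Years 1–4 | Share missing |
|---|---|---|---|---|---|---|
| 3600 | 1661.3 | 3073.5 + 2768.9 + 2768.9 | 8611.3 | 8611.3 | 10,272.6 | 16.2% |
| 3000 | 1384.5 | 3 × 2768.9 | 8306.7 | 8306.7 | 9691.2 | 14.3% |
| 4000 | 1845.9 | 3415.0 + 2902.7 + 2768.9 | 9086.6 | 9086.6 | 10,932.6 | 16.9% |

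(The last total is summed before rounding.) The replacement counts also match the printed columns: 225/450/450 for 3000 subjects and 327 after Year 3 for 4000. Other readings do not give 8611.3: Years 1–3 give 7503.7, and six sites for 3 years give 6 × 1486.0 = 8916.0.

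**Interval.** 95% CI = r ± 1.96 × √(1.8 × r / PY), with r = 0.009, scaled to 1000.

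- PY = 3322.7: half-width 4.33, [4.7 ; 13.3], as printed.
- PY = 8611.3: half-width 2.69, 6.31 to 11.69, as printed; 0.009 × 8611.3 = 77.5 cases (printed 78).
- PY = 10,272.6: half-width 2.46, 6.54 to 11.46, so [6.5 ; 11.5]; 0.009 × 10,272.6 = 92.5 cases.
- PY = 9691.2 (3000 subjects): 6.47 to 11.53, so [6.5 ; 11.5]; printed [6.3 ; 11.7].
- PY = 10,932.6 (4000 subjects): 6.61 to 11.39, so [6.6 ; 11.4]; printed [6.4 ; 11.6].

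**Sensitivity to the replacement floor.** The table's overall rows top up to a pooled 3000, whereas the recruitment rule is 500 per site. From the 600-subject site rows, 3 × 1947.5 + 3 × 1486.0 = 10,300.5 person-years, 27.9 more than 10,272.6. The interval is the same.

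**Sensitivity to drop-out.** At 20%, f = 0.89628.

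- 3600 subjects: 9948.8 person-years, 89.5 cases, 6.50 to 11.50, still [6.5 ; 11.5].
- 3000 subjects: 1344.4 + 3 × 2688.9 ≈ 9411 person-years, 6.43 to 11.57, so [6.4 ; 11.6].

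**The case against.** The case on the other side accepts the arithmetic and questions its importance.

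- **Little depends on these rows.** The error understates precision by about 0.2 per 1000 at each limit. The 600 per site comes from a target of 500 active subjects and the drop-out range, and there is no hypothesis test. The primary objective is incidence by year or season, for which the one-year interval is the relevant figure. All of this stands.
- **Events have overtaken it.** SAP Amendment 1 (sections 1, 2.1 and 7.2.2.1) records early termination, a planned site that never opened, and a change of method that ignores household clustering. Correcting Table 15 alters no reported estimate. This also stands, so the point concerns the plan only.
- **10,272.6 is itself idealised.** It takes the low end of the drop-out range, a pooled top-up and expansion entry on the first day of Year 2. This is fair, but 8611.3 rests on the same assumptions, so they do not explain the gap.
- **The rows could simply be relabelled as Years 2 to 4.** That would remove the contradiction, but it does not fit the documents. The text and the table both say 4 years, section 8.5.2 counts time from enrolment, and the 3000-subject row lists 225 replacements after Year 1. Year 1 was therefore modelled and its person-time left out of the sum.

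**Conclusion.** The concern holds. The overall 4-year blocks of Table 15 and the interval [6.3 ; 11.7] contradict the protocol's follow-up plan and the table's own site rows. For 3600 subjects the half-width falls from 2.69 to 2.46 per 1000, about 8% narrower, once Year 1 is included.

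The contradiction itself needs no assumption, since it follows from the printed site rows. The corrected totals assume 15% annual drop-out (inferred, because it reproduces the table to the decimal), expansion entry at the start of Year 2, and the table's replacement floors. The rounded 3600-subject interval at 9 per 1000 is the same at 15% and 20% drop-out; the 3000-subject interval is not. This is a conservative error in a stated planning figure. It is worth correcting and has no consequence for enrolment or analysis.

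**What to change.** Restate the three overall 4-year blocks of Table 15 and the matching sentence of 8.2.3. Name the drop-out rate used, and say whether the replacement floor is pooled or per site. At 15% with the pooled floor, the design-effect intervals per 1000 person-years are:

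| Incidence | 3600 subjects (10,272.6 PY) | 3000 subjects (9691.2 PY) | 4000 subjects (10,932.6 PY) |
|---|---|---|---|
| 3 | [1.6 ; 4.4] | [1.5 ; 4.5] | [1.6 ; 4.4] |
| 6 | [4.0 ; 8.0] | [3.9 ; 8.1] | [4.1 ; 7.9] |
| 9 | [6.5 ; 11.5] | [6.5 ; 11.5] | [6.6 ; 11.4] |
| 12 | [9.2 ; 14.8] | [9.1 ; 14.9] | [9.2 ; 14.8] |
| 15 | [11.8 ; 18.2] | [11.7 ; 18.3] | [11.9 ; 18.1] |

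The case counts, exact Poisson limits and unadjusted normal limits in these blocks must be recomputed from the same person-years. If the per-site floor is preferred for 3600 subjects, use 10,300.5 person-years; the interval at 9 per 1000 does not change. The cost is fifteen table rows and one sentence.
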